The current project seeks to build on past progress by further developing and refining the booster. In particular, the current project is an extension of previous work by expanding the investigation into complete social networks (students involved in Greek life). This booster contains feedback about alcohol use tailored to the recipient, and will be emailed 2, 6, 10, and 14 weeks after baseline (experimental condition), or not at all (control condition). This study will be conducted specifically with students who are members of fraternities or sororities (specifically, those in the organizations that agree to participate). This population engages in heavy alcohol use, so is ideal for an alcohol intervention. Members of fraternities and sororities (i.e., "Greek life") engage in more frequent drinking, consume more when drinking, and have higher peak drinking occasions than students not involved in Greek life. We aim to administer the intervention and associated booster among complete networks of Greek organizations to examine how the intervention and booster progress through social networks. Moreover, given the close connections among members of fraternities and sororities, these may be closed peer networks that could facilitate the examination of how changes in drinking occur through social influence. In other words, we can potentially examine if change happens through selection (i.e., transitioning into friendships with individuals who are similar), such that those who drink less after the intervention change who they drink with to those individuals in the organization who also drink less; or socialization (i.e., becoming more similar to individuals who one spends time with), or drinking less through peer influence because participants may drink less to match the individuals they drink with, who are drinking less after the intervention and booster.

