Thus, the current study has two primary aims (to be examined regardless of study outcomes or participation rates) and an exploratory, secondary aim (to be examined only if the booster is efficacious and the majority of members for each organization enrolled complete the study). Primary Aim 1: We will examine the efficacy of a personalized feedback booster emailed after eCHECKUP TO GO for Alcohol among members of fraternities and sororities. We expect initial post-intervention drinking reductions for both study conditions, with individuals in the booster condition reporting further reductions at later follow-ups. Primary Aim 2: Given the focus on perceived descriptive norms and protective behavioral strategies in the personalized

feedback boosters, we will examine if the booster impacts changes in those constructs over time. We expect individuals in the booster condition will report further reductions in norms and increases in protective behavioral strategies at later follow-ups. Exploratory, Secondary Aim: If the emailed booster is efficacious and the majority of members for each organization enrolled complete the study, we will examine social mechanisms of change (i.e., through selection versus socialization).

Participant population

Eligible participants must 1) be 18 years of age or older, 2) be an undergraduate student at a participating institution; and 3) be a member of a participating fraternity or sorority. Power analyses were conducted using Monte Carlo simulation methods within Mplus (version 5.21, Muthén & Muthén, 2002). Effect sizes, variance, and covariances used were based on data from a preliminary study with a similar protocol (some participants receiving the intervention only, others receiving the intervention plus booster) among college drinkers (Braitman & Henson, 2016; Braitman & Lau-Barraco, 2018). We estimated a retention rate of 76%, the average reported in a meta-analysis of RCTs assessing alcohol interventions for first-year college students (Scott-Sheldon et al., 2014). Monte Carlo simulation methods indicated that for the effect size expected ($b = 6.57$, $\beta = 0.537$) and for the expected 24% attrition, a sample size of $N = 180$ total students should yield sufficient power (.80+) to detect booster effects.

Recruitment Procedure

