Boosters: After the intervention, participants receive additional emails from the researcher, depending on their study condition. For the intervention-plus-booster study condition, these emails contain personalized normative feedback about alcohol use as well as feedback about harm reduction strategies, serving as a booster to the original intervention. Baseline data are used to provide students with normative information (e.g., typical drinking among ODU students who are male/female), and reminders of protective behavioral strategies they can use to reduce drinking-related harm (separated by strategies they have reported using recently versus those they might consider trying). This is received at 2 weeks, 6 weeks, 10 weeks, and 14 weeks after baseline. Participants in the intervention-only control condition do not receive any feedback via email. Participants are assigned to study condition at the group level, so that an entire organization receives the booster emails (or the entire organization does not).

Measures

The same measures are included in baseline and the follow-up surveys:

Participants' **alcohol use** is assessed using a modified version of the Daily Drinking Questionnaire for the past 30 days (Collins et al., 1985). Additionally, participants describe specific aspects regarding their drinking in the past 30 days (e.g., highest consumption in a single day). **Descriptive Norms** are assessed by modifying the DDQ to reflect their expectations for typical male students at the same institution, typical female students at the same institution, and

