## **Statistical Analysis Plan**

Prior to hypothesis testing, the data will be examined for normality and outliers. Histograms and values for skewness and kurtosis will be examined. Positively skewed variables will be natural log transformed, unless paired with an excessive number of zeroes. If there are an excess of zeroes in an outcome, the variable will be dichotomized if other values are not well represented, or appropriate modeling techniques will be used (e.g., hurdle models) if other values are well represented. Boxplots will be used to check for outliers. Extreme values will be winsorized (i.e., cases retained in the sample, but values made less extreme). Cases with missing data will be compared to complete cases across major study variables to identify if there are systematic differences in missingness. If significant associations are identified, these variables will be used as covariates in later analyses.

To address Primary Aim 1 of the study, the data will be analyzed using latent growth models within a structural equation modeling framework. Separate models will be conducted for each alcohol outcome: alcohol consumption (e.g., quantity), and alcohol-related problems. It is not known the exact trajectory across time (baseline, 1 month, 3 months, 6 months), so a few models will be compared to identify which best captures the shape of change over time. A simple model that reflects change to 1 month (slope 1; initial change post-intervention) and longer-term maintenance (slope 2; linear growth to 9 months) will be compared to models with additional curvilinear components in case longer-term maintenance is not a linear process. Study condition will be dummy coded with “no booster” as the category of reference, and will serve as a predictor of each latent variable (latent intercept, each slope). All models will be conducted using maximum likelihood estimation, and will control for sex. The model for problems will also control for alcohol quantity.

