Given that the tailored feedback boosters address both descriptive drinking norms and protective behavioral strategies, these are considered secondary outcomes. Models identical to the one described above will be conducted (e.g., latent growth models with two slopes, regressed on study condition), but with norms and protective behavioral strategies serving as the outcomes of interest rather than alcohol use or related problems (addressing Primary Aim 2). Given prior findings that emailed booster feedback containing personalized normative feedback and protective behavioral strategies (PBS) was significantly more effective for select groups (i.e., those lower in PBS use [Braitman & Henson, 2016], legal age drinkers [Braitman & Lau-Barraco, 2018]), we will examine potential moderators of booster efficacy as a supplementary exploratory analysis. Legal drinking status by age (coded as 1 = *age 21-24* [legal], 0 = *age 18-20* [underage]) and baseline PBS use (in its original continuous metric) will be explored as potential moderators. The moderator and its interaction with study condition will be added as predictors of each latent factor (latent intercept, slope 1, and slope 2). All models will be conducted in Mplus (version 8; Muthén & Muthén, 1998–2019) using maximum likelihood estimation.

For the Exploratory, Secondary Aim, RSIENA will be used to conduct stochastic, actor-based models (Ripley et al., 2017). These will allow us to examine if behavior change precedes network changes (i.e., selection), or if network changes precede behavior change (i.e., socialization). These models will only be conducted if reductions in drinking or related problems are evidenced in the Primary Aim 1 examination (i.e., there is behavior change over time), and if several members of each organization participate (so network change can be examined over time).

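### Whole organizations are assigned to condition, but the Aim 1 and Aim 2 models ignore organization, so standard errors for the booster effect are too small if change correlates within organizations

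*SAP*

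**What the plan says.** **Assignment.** Protocol, Study Procedure (Boosters): "Participants are assigned to study condition at the group level, so that an entire organization receives the booster emails", or the entire organization does not. Condition therefore varies only between organizations.

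**Aim 1 model.** The Statistical Analysis Plan fits latent growth models to student data. Study condition is a dummy variable that "will serve as a predictor of each latent variable (latent intercept, each slope". On estimation and covariates: "All models will be conducted using maximum likelihood estimation, and will control for sex". For alcohol-related problems there is one addition: "The model for problems will also control for alcohol quantity". Variables found to be related to missingness may also be added.

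**Aim 2 and moderators.** For norms and protective behavioral strategies, "Models identical to the one described above will be conducted". The moderator models add interactions with condition and again use maximum likelihood.

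**Power.** Protocol, Participant population: N = 180 "total students should yield sufficient power (.80+) to detect booster effects", with 24% attrition and an expected effect of b = 6.57, β = 0.537. On the inputs: "Effect sizes, variance, and covariances used were based on data from a preliminary study with a similar protocol". No ICC, design effect or number of organizations is given.

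**Expected dependence.** Protocol, Primary Aims: "given the close connections among members of fraternities and sororities, these may be closed peer networks". That section goes on to describe members' drinking becoming more alike through socialization.

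**The concern.** When whole organizations are assigned, the evidence on the booster comes from comparing organizations. The planned models judge the effect against student-to-student variation, as if each student had been assigned separately. The latent intercept and slopes account for correlation within a student over time, but not for correlation between students of one organization.

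Nothing else in the plan fills the gap:

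- Sex may absorb a fraternity-sorority difference, but not differences among organizations of the same type.
- Alcohol quantity and predictors of missingness do not stand in for a cluster term.
- The RSIENA network models are exploratory and conditional, and they do not estimate the Aim 1 or Aim 2 booster effect.

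At stake is the main claim of the trial. A chance difference between chapters could be reported as booster efficacy, on both primary aims.

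**Working it through.** **Inputs from the documents.** N = 180 and 76% retention, so 180 × 0.76 = 136.8 completers; β = 0.537; power of .80 or more.

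**Assumptions, because the documents are silent.** K equal-sized organizations split 1:1, K = 4 to 18; ICC of change (after sex) 0.01 to 0.10; two-sided α = 0.05.

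**Step 1: the stated power.** The Monte Carlo variances and covariances are not given, so N = 180 cannot be reproduced exactly. If β is read as a standardized mean difference, 136.8 independent students give 0.537/√(4/136.8) = 3.14, and power Φ(3.14 − 1.96) = 0.88. That agrees with the stated .80 or more, with no allowance for clustering.

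**Step 2: type I error when organization is ignored.** With m = 136.8/K, the design effect is DEFF = 1 + (m − 1) × ICC. The unadjusted standard error is too small by a factor √DEFF, so the true type I error is 2 × [1 − Φ(1.96/√DEFF)].

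For K = 8 and ICC 0.05: m = 17.1; DEFF = 1 + 16.1 × 0.05 = 1.81; √DEFF = 1.34; 1.96/1.34 = 1.46; type I error about 14%.

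| K | m | DEFF at ICC 0.05 | Type I error, ICC 0.01 | ICC 0.02 | ICC 0.05 | ICC 0.10 |
|---|---|---|---|---|---|---|
| 4 | 34.2 | 2.66 | 9% | 13% | 23% | 35% |
| 6 | 22.8 | 2.09 | 8% | 10% | 18% | 27% |
| 8 | 17.1 | 1.81 | 7% | 9% | 14% | 23% |
| 12 | 11.4 | 1.52 | 6% | 7% | 11% | 17% |
| 18 | 7.6 | 1.33 | 6% | 7% | 9% | 13% |

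**Step 3: simulation checks.**

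- *Two-group comparison of change*, 8 organizations, 20,000 runs per case. Ignoring organization gave 5.1% at ICC 0, then 6.8%, 9.1%, 14.5% and 23.1% at ICC 0.01, 0.02, 0.05 and 0.10. A test on organization means stayed near 5% throughout. The inflation therefore comes from the clustering.
- *Slope 2 of a two-slope growth model*, with stable organization differences in level, complete data at 0, 1, 3 and 6 months, and 4,000 null trials per case. At ICC 0.05, ignoring organization gave 25%, 18%, 16%, 12% and 10% for K = 4, 6, 8, 12 and 18. A sex-adjusted organization-level test with K − 3 degrees of freedom gave 4-5% in all 15 combinations of K and ICC (0.01, 0.05, 0.10).
- *Condition-by-moderator interactions*, at ICC 0.05. The rate was 5-6% if the moderator's effect is the same in every organization, and 6-11% if it varies between organizations with the same variance.

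**Step 4: power of a valid test.** Noncentral t with K − 3 degrees of freedom and noncentrality 0.537/√(4 × DEFF/136.8):

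| K | Power, ICC 0.01 | Power, ICC 0.05 |
|---|---|---|
| 4 | 0.17 | 0.12 |
| 6 | 0.49 | 0.33 |
| 8 | 0.65 | 0.47 |
| 12 | 0.76 | 0.62 |
| 18 | 0.81 | 0.72 |

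These values depend on the reading of β. If β is fully standardized on a 1:1 dummy (SD 0.5), the difference is 0.537/0.5 = 1.07. Power at ICC 0.05 is then 0.24, 0.81, 0.96, 0.99 and 1.00.

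**The case against.** The strongest objection is that the size of the error is undetermined. Neither K nor the ICC is in the documents, and nothing supports 0.05 over another value. At ICC 0.01 the type I error is only 6-9%, and at ICC 0 the planned analysis is valid. This stands for the magnitude, but not for the omission: the plan neither argues that the ICC is negligible nor proposes to check it, and the protocol gives reasons to expect otherwise.

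Other points have partial force:

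- **Power.** The low figures follow from one reading of β. Under the fully standardized reading, power is adequate from about 6 organizations at ICC 0.05. That reading would, however, put a simple two-group comparison of independent students far above the stated .80. The power figures are illustrative.
- **Simulation.** It simplifies the planned model: complete data, assumed variance components, regression of estimated slopes, and a last visit at 6 months, although the documents also mention 9 months. The formula and the separate two-group simulation give the same picture without the growth model.
- **Remedy.** An organization-level test is one option among several. If limited to completers, it would discard partial data that likelihood methods use, with 24% attrition expected.
- **Unseen text.** The part of the SAP before the Statistical Analysis Plan heading was not available for this review. The modelling text begins under that heading, so an unseen cluster adjustment is unlikely but cannot be excluded.

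**Conclusion.** The concern holds and must be fixed before the booster effect is tested. Assignment is by organization, and the analysis as written treats students as independent. Whenever change correlates positively within organizations, the standard errors for the booster effect are too small in both primary aims.

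Confidence is high on the omission and its direction. The size is conditional: about 9-23% true type I error at an assumed ICC of 0.05 with 18 down to 4 organizations, and 6-35% over ICCs of 0.01 to 0.10, assuming 137 completers, equal-sized organizations and 1:1 allocation. Moderator interactions are less affected. Dichotomized and hurdle outcomes were not simulated.

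**What to change.** 1. **Model.** Analyse Aims 1 and 2 and the moderators with organization as the cluster level, for example a two-level growth model with a small-sample correction. Test condition with organization-based degrees of freedom.
2. **Few organizations, or dichotomized or hurdle outcomes.** Make a sex-adjusted organization-level test of change with K − 3 degrees of freedom the primary test, using all available visits and not only completers. With 4 organizations this leaves 1 degree of freedom, and the SAP should acknowledge that limit.
3. **Robust errors.** Do not rely on uncorrected sandwich errors (the COMPLEX/MLR route in Mplus) with few organizations.
4. **Permutation test.** Use one only if allocation was random and p < 0.05 is attainable. With equal arms and no stratification the smallest two-sided p is 2/C(K, K/2): 0.33 for K = 4, 0.10 for K = 6, 0.029 for K = 8. If allocation was stratified by sex with equal strata, it is 2/C(K/2, K/4)²: 0.056 for K = 8 and 0.005 for K = 12.
5. **Reporting.** State the number and sizes of organizations per arm, how they were allocated, and the ICC of change. State how β = 0.537 is standardized, and restate the power for N = 180 allowing for clustering.

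**Cost.** The analysis change needs SAP text and a different model, with no new data. Intervals will be wider and the stated power will probably fall. If the restated power is inadequate, the sponsor must either recruit more organizations, which does mean new data, or state that the trial is underpowered.
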